5.4 Treatment duration

The Part 1 study consists of a screening period (within 28 days prior to randomization) and a treatment period of 6 cycles (28 days/cycle, 24 weeks in total). The primary endpoint analysis will be performed after the last patient has completed Week 25 follow-up and tumor assessments (including Investigator assessment and BIRC assessment).

The Part 2 study consists of a treatment period of 6 cycles (28 days/cycle, 24 weeks in total). Patients who complete Part 2 treatment will be eligible to enter Part 3 to continue a longer period of treatment and safety follow-up.

Part 3 is an extension treatment phase. All patients will continue to receive open-label ABSK021 continuously (28 days per cycle) until any of the following events occur: disease progression, experiencing unacceptable toxicity, withdrawal of informed consent form, commercialization of the study drug for the treatment of TGCT approved by the local regulatory authorities, decision by the sponsor to terminate the study, or until 2 years after the last patient enters Part 3, whichever

occurs first.

5.5 Dose Modification

For patients who cannot tolerate the protocol-specified dosing schedule, dose modifications (dose interruption or dose reduction) are allowed to enable the patients to continue study treatment. All dose modifications should be based on the worst toxicity that occurred previously (CTCAE Version 5.0). A maximum reduction of one dose level to 25 mg QD is allowed. If any patient requires a therapeutic dose lower than 25 mg QD, the study drug must be discontinued and the patient must end the treatment (EOT) and accept safety follow-up visit. All dose interruptions or modifications must be documented in the eCRF.

5.5.1 Dose interruption due to unscheduled medical procedures

If a patient requires unscheduled surgery or other unscheduled medical procedures during the study, the Investigator should discuss with the sponsor to determine whether study drug interruption is required.

5.5.2 Dose interruption or modification due to intolerance or ADRs

The study drug administration may be interrupted or modified (i.e., dose reduction) at the discretion of the study personnel, e.g. in the event of an AE, or for other reasons after consultation with the sponsor. All dose modifications should be based on the worst toxicity that occurred previously. The dose modification guidelines described in Table 5 are recommended only and comprehensive judgement can be made by the Investigator based on the actual situation of the patient. Considering that some AEs may be related to the mechanism of action of the drug, the Investigator should have a prospective discussion with the sponsor whenever possible.

If the AE leading to dose modification recovers to Grade 1 or baseline within 14 days, the patient may continue to receive the same dose level at the time of the AE onset or restart the treatment at 1 dose level lower (to 25 mg QD).

If an AE leading to dose modification does not recover to Grade 1 or baseline within 14 days, discussion with the sponsor is required, and treatment may be restarted at one dose level lower (to 25 mg QD) if the Investigator considers the event to be clinically insignificant.

Dose interruptions due to non-AE causes (such as irresistible factors such as drug dispensing interruption due to epidemic quarantine) are not patient to the above conditions. Please discuss the details with the sponsor in advance.

In case of any inconsistency with the dose modification specified in the protocol, the Investigator is advised to discuss and confirm with the sponsor in advance. Patients who have dose interruption or permanently discontinue treatment due to adverse events or clinically significant laboratory abnormalities are recommended to be followed weekly (more frequent visits are

allowed as required by the study site or as clinically indicated) until the AE resolves or stabilizes, whichever occurs first.

Table 5 Dose Modification Guidelines

Toxicity Grade (Per CTCAE 5.0)	Dose Modification Recommendations
ALT/AST increased	
Grade 2	Hold study drug, administer appropriate supportive care or treatment, and monitor liver function at least once weekly until recovery to \leq Grade 1 or baseline, 
 – Restart at the same dose level if recovered within 14 days; in the event of 2 relapse, restart at one dose level lower or discuss with the sponsor. – Restart at one dose level lower if recovered after 14 days; in the event of 2 relapse, discussion with the sponsor is required.
Grade 3	Hold study drug, administer appropriate supportive care or treatment, and monitor liver function at least once weekly until recovery to \leq Grade 1 or baseline, 
 – Restart at one dose level lower if recovered within 14 days; subsequent recurrence of Grade 3 AEs should be discussed with the sponsor. – If recovered after 14 days, discussion with the sponsor is required.
Grade 4	Permanently discontinue the study drug.
Bilirubin increased	
Grade 2	Hold study drug, administer appropriate supportive care or treatment, and monitor liver function at least once weekly until recovery to \leq Grade 1 or baseline, 
 – Restart at one dose level lower if recovered within 14 days; subsequent recurrence of Grade 2 AEs should be discussed with the sponsor. – If recovered after 14 days, discussion with the sponsor is required.
\geq Grade 2 Concurrent ALT or AST elevation \geq Grade 3	Permanently discontinue the study drug.
Grade 3 or 4	Permanently discontinue the study drug.
CK increased	

Grade 2	
Closely monitor clinical symptoms (abnormal renal function or signs of myocardial and skeletal muscle injury) and continue study drug at the current dose. Hold study drug and monitor CK levels at least once a week until recovery to \leq Grade 1 or baseline if accompanied with clinical symptoms.
 
 – If recovered within 14 days, restart at the same dose level. – If not recovered within 14 days, discussion with the sponsor is required. 
If recurrence of \geq Grade 2 accompanied with clinical symptoms after restart dosing, discussion with the sponsor is required.

Grade 3	
Closely monitor clinical symptoms (abnormal renal function or signs of myocardial and skeletal muscle injury) and continue the treatment at the current dose level if without clinical symptoms. If need, monitor CK levels at least once weekly until recovery to \leq Grade 1 or baseline, or until the investigators assesses that CK monitor can be discontinued. If clinical symptoms accompanied, hold the study drug.
 
For patients with asymptomatic CK increased:
 
 – If recovered within 14 days, restart at the same dose level; subsequent recurrence of Grade 3 AE should be discussed with the Sponsor. – If not recovered within 14 days, discussion with the sponsor is required. 
For patients with CK increased associated with clinical symptoms:
 
 – Restart at a reduced dose after recovered to Grade 1 or baseline. If recurrence of \geq Grade 2 accompanied with clinical symptoms after restart dosing, discussion with the Sponsor is required.
Grade 4	
Hold study drug and closely monitor clinical symptoms (signs of abnormal kidney function or heart and skeletal muscle damage), and monitor CK levels at least once weekly until recovery to \leq Grade 1 or baseline.
 
For patients with asymptomatic CK increased:
 
 – If recovered within 14 days, restart at the same dose level or 1 dose level lower. – If not recovered within 14 days, discussion with the sponsor is required. 
For patients with CK increased associated with clinical symptoms:
 
 – Restart at a reduced dose after recovered to Grade 1 or baseline. If recurrence of \geq Grade 2 accompanied with clinical symptoms after restart dosing, discussion with the Sponsor is required.
Non-hematologic toxicity (except ALT/AST, bilirubin, or CK increased)	
Grade 1	Administer appropriate supportive care or treatment and continue study drug at the current dose.

Grade 2	
Administer appropriate supportive care or treatment and continue study drug at the current dose.
 
Hold study drug if not improved within 7 days:
 
 – If the AE recovers to Grade 1 or baseline within 14 days, restart at the same dose level. – If the AE recovers to Grade 1 or baseline after 14 days, restart at one dose level lower. 
If the AE relapses to Grade 2 after resuming dosing, discussion with the sponsor is required.

≥ Grade 3	
Administer appropriate supportive care or treatment and hold study drug:
 
 – If the AE recovers to Grade 1 or baseline within 14 days, restart at the same dose level lower. – If the AE recovers to Grade 1 or baseline after 14 days, discussion with the sponsor is required. 
Permanently discontinue study drug if the AE relapses to ≥ Grade 3 after resuming dosing. If, in the opinion of the Investigator, it is in the best interest of the patient to resume dosing, it must be discussed with the sponsor to determine whether the study drug can be restarted.

Grade 4	
Administer appropriate supportive care or treatment and hold study drug:
 
 – If the AE recovers to Grade 1 or baseline within 14 days, restart at the same dose level lower. – If the AE recovers to Grade 1 or baseline after 14 days, permanently discontinue study drug. If, in the opinion of the Investigator, it is in the best interest of the patient to resume dosing, it must be discussed with the sponsor to determine whether the study drug can be restarted.
Hematologic toxicity	
≤ Grade 2	Administer appropriate supportive care or treatment and continue treatment with study drug at the current dose.
≥ Grade 3	
Administer appropriate supportive care or treatment and hold study drug:
 
 – If the AE recovers to Grade 1 or baseline within 14 days, restart at the same dose level. – If the AE recovers to Grade 1 or baseline after 14 days, restart at one dose level lower. 
If the AE relapses to ≥ Grade 3 after resuming dosing, it should be discussed with the sponsor.

Note: dose level reductions will be determined based on the dose level at the onset time AE.

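### Protocol Table 5 contains two contradictory dose-modification instructions and one ambiguous one, so three situations have no single written rule

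*Protocol*

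**What the plan says.** All three places are in Table 5 of Protocol Section 5.5.2.

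**Non-hematologic toxicity other than ALT/AST, bilirubin or CK.** There is a row for ≥ Grade 3 and, below it, a separate row for Grade 4.
- Early recovery (within 14 days) is worded identically in both: "restart at the same dose level lower".
- Late recovery, ≥ Grade 3 row: "If the AE recovers to Grade 1 or baseline after 14 days, discussion with the sponsor is required".
- Late recovery, Grade 4 row: "If the AE recovers to Grade 1 or baseline after 14 days, permanently discontinue study drug". An exception follows: if the investigator thinks resuming is in the patient's best interest, this must be discussed with the sponsor.
- Relapse, ≥ Grade 3 row only: "Permanently discontinue study drug if the AE relapses to ≥ Grade 3 after resuming dosing", again with a best-interest exception through the sponsor.

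**CK increased, Grade 3.** The row first says to "continue the treatment at the current dose level if without clinical symptoms" and to hold drug only when symptoms are present. Under the asymptomatic sub-heading it then says: "If recovered within 14 days, restart at the same dose level; subsequent recurrence of Grade 3 AE should be discussed with the Sponsor".

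**Surrounding text.** Section 5.5 allows one reduction, to 25 mg QD, and requires discontinuation if a lower dose is needed. Section 5.5.2 describes Table 5 as a recommendation subject to investigator judgement. For recovery within 14 days it allows either the unchanged dose or one level down. For later recovery it requires sponsor discussion and allows a restart one level down if the investigator judges the event clinically insignificant. It advises confirming inconsistencies with the sponsor in advance.

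**The concern.** A dose-modification table should take a site from event, grade and recovery time to one instruction. In three places this one does not. Two are contradictions: the overlapping Grade 4 rows, and the continue-then-restart wording for CK. The third, the restart phrase, is an ambiguity.

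These are safety instructions applied under blinding across many sites. Two investigators with the same event could reasonably do different things, and both would be following the table. The reading chosen can change a patient's exposure and whether the patient stays on drug. It also feeds outputs that the plan reports: dose modification is a named safety endpoint (Protocol 2.2.3), and SAP 5.6.3 and 7.2.4 tabulate reductions, interruptions and TEAEs leading to discontinuation. The effect can persist, because a dose modified in Part 1 carries into Part 2 (Protocol 3.1) and the Part 3 starting dose follows from the dose at the end of Part 2 (Protocol 5.1.2).

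**Working it through.** No sample-size, power or alpha figure is involved. The check sets the instructions side by side.

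**1. Grade 4 non-hematologic event**

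| Situation | ≥ Grade 3 row | Grade 4 row | Section 5.5.2 general text |
|---|---|---|---|
| Recovery within 14 days | Restart (ambiguous phrase) | Same phrase | Unchanged dose or one level down |
| Recovery after 14 days | Sponsor discussion | Permanent discontinuation, unless resumption is discussed with the sponsor | Sponsor discussion; one level down if clinically insignificant |
| Relapse to ≥ Grade 3 after restart | Permanent discontinuation, with sponsor exception | No rule | No rule |

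Grade 4 satisfies both row labels. The rows agree for early recovery. They differ in the default for late recovery and in whether a relapse rule exists.

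**2. The restart phrase**

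Elsewhere the table treats an unchanged dose and a one-level reduction as separate instructions, and where both are allowed (asymptomatic CK Grade 4) it names both. The phrase matches none of these forms. Neighbouring rows do not settle it. For recovery within 14 days, non-hematologic Grade 2 and hematologic ≥ Grade 3 use the unchanged dose, while ALT/AST Grade 3 uses one level down. The consequences are:
- Patient on 50 mg QD: 50 mg or 25 mg QD.
- Patient already on 25 mg QD: 25 mg QD, or discontinuation, since Section 5.5 allows nothing lower.

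**3. Asymptomatic Grade 3 CK**

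The first instruction means no interruption. The second presupposes one. In the CK Grade 4 row the same sequence is coherent, because there the drug is held in every patient first. In the Grade 3 row a hold is instructed only when symptoms are present.

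**4. Frequency**

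The documents give no rate for any of these exact situations. The nearest figure is in Protocol 1.2.2: as of June 2022, 3/33 = 9.1% of Phase 1 TGCT patients had any Grade ≥ 3 TEAE, and 1/33 = 3.0% had one regarded as drug-related. Those counts cover all event types and both doses, over a mean of 111 days. Part 1 lasts 24 × 7 = 168 days, and Parts 2 and 3 add more, so they are context rather than a bound.

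**The case against.** The strongest reply is that Table 5 was never meant to be applied mechanically. Section 5.5.2 makes it advisory, leaves room for judgement and points to the sponsor when something is inconsistent. For early recovery the general rule permits both readings of the restart phrase, except that no level exists below 25 mg QD. Under both Grade 4 readings, a restart after late recovery involves the sponsor. For asymptomatic Grade 3 CK, both sentences end at the current dose, and study personnel may interrupt at their discretion, so the restart line could apply to a drug that was held for that reason. The table is the same for both blinded arms, and the primary estimand handles dose modification due to toxicity by treatment policy (Protocol 7.4.4.1).

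Most of this stands, and it limits the weight of the point. It does not remove it. The advisory text gives a route for settling a case but does not say which instruction the table recommends. Confirmation with the sponsor is only advised, and that sentence can also be read as covering departures from the table rather than conflicts within it. The general rule does not resolve the late-recovery default, the missing relapse rule or the CK wording.

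A reader might infer that the disputed lines will be used very often by scaling the December 2022 Phase 1 rates to 60 ABSK021 patients: 33/49 × 60 ≈ 40 with CK increase and 14/37 × 60 ≈ 23 with interruption. The documents do not support that. The 33/49 is CK increase of any grade, pooled over 25 and 50 mg, whereas the CK defect concerns asymptomatic Grade 3 only. The 14/37 is interruption for any TEAE at 50 mg over a median of 9.3 months, including interruptions under rows that are not in question.

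**Conclusion.** The point holds: Table 5 has two internal contradictions and one ambiguous instruction, all in the current text. The Grade 4 conflict is confined to recovery after 14 days and to the relapse rule. The restart ambiguity is a choice between 50 and 25 mg QD or, at 25 mg, between staying on drug and stopping. The CK conflict is whether there is an interruption at all.

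The effect falls on exposure, discontinuation, the descriptive dose-modification summaries and the dose carried forward. It would be too strong to infer that sites have no way to act, or that the efficacy conclusions are at risk. The sponsor route exists, and no power, alpha or primary-estimand figure is affected. How many patients will meet these exact situations cannot be estimated from the documents. The conclusion rests on the wording alone and takes no position on which clinical rule is right.

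**What to change.** The sponsor should reconcile the three passages of Table 5 with each other and with Sections 5.5 and 5.5.2, so that each event grade and recovery time leads to one instruction. That means:
- making clear which row governs a Grade 4 non-hematologic event, including after relapse;
- replacing the restart phrase in each row with wording that has one meaning, including for a patient already on 25 mg QD;
- making the continue and restart statements for asymptomatic Grade 3 CK consistent, by removing one or by stating when each applies.

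Which clinical rule applies in each case is the sponsor's decision. The cost is a protocol clarification and a letter to sites. The sample size and the primary analysis need no change.

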5.6 Randomized Treatment Assignment

After the Investigator has confirmed that the patient meets all eligibility criteria, in Part 1 of the study, patients will be randomized in a 2:1 ratio to ABSK021 treatment or matching placebo according to the randomization schedule provided by an independent statistician. Randomization will be performed between all sites using a central interactive web response system (IWRS). Randomization will be stratified by China sites and non-China sites.

At screening, the IWRS will assign a unique screening number to each patient. The screening number will be used in all study-related documents, including the electronic case report form (eCRF). The screening number will not be reused. In addition, a randomization number will be assigned to each screened eligible patient. This randomization number correlates the patient's eCRF and the assignment of treatment group.

If a patient does not receive study drug according to the assigned treatment group, the reason must be clearly documented in the eCRF. The patient may still participate in the study and continue to receive the same study drug, and all data will be collected for this patient and subsequent follow-up will be performed according to the study schedule.

The first dose of study drug (Part 1-C1D1) should be administered within 3 days of the date of randomization.

In Part 2 of the study, all patients will receive open-label treatment with ABSK021.

5.7 Blinding and Unblinding

5.7.1 Blinding

Part 1 will be a randomized, placebo-controlled, double-blind study, where treatment assignment will remain unknown to the patients, Investigators, study site personnel, safety laboratory personnel, central imaging readers and reviewers, and the sponsor. The appearance of ABSK021 and placebo capsules will be identical.

5.7.2 Unblinding

5.7.2.1 Emergency Unblinding

In case of emergency where, in the opinion of the Investigator, immediate unblinding of treatment is necessary in order to evaluate further course of action, the Investigator should access the IWRS to initiate patient unblinding. Whenever possible, the Investigator should communicate emergency unblinding with the sponsor as early as possible. Under the premise of the patient's safety, the unblinding should be limited to the minimum number of personnel.

The Investigator should enter in the IWRS system:

- Confirm to continue with unblinding
- Patient ID

The IWRS will provide:

- Patient's randomized treatment group
- IWRS transaction confirmation

The Investigator may also contact the sponsor's medical monitor for information related to ABSK021 adverse effects in making the decision to unblind. It is important to note that, once unblinded, a patient cannot receive further study treatment and must discontinue from the study.

The Investigator should promptly document and report to the Sponsor any unblinding for emergency reasons (e.g., accidental unblinding, unblinding due to SAE, etc.).

In the event of an emergency unblinding, the date and reason for unblinding must be fully documented in the source document and eCRF. The Investigator should make every effort to ensure that study site personnel do not mention patient treatment group assignment to sponsor staff or relevant personnel involved in the conduct of the study.

5.7.2.2 End of Part 1 Unblinding

After completing the assessments of Part 1, patients who meet eligibility criteria and are willing to continue in the open-label study (Part 2) may receive open-label ABSK021. After all patients complete Part 1 and reach the primary efficacy analysis time point, unblinding (for the sponsor and contract research organizations only) and analysis will be performed after data cleaning and database lock.

5.8 End of Study and Treatment Discontinuation

The study consists of Part 1, Part 2 and Part 3. In Part 1, all patients who have completed 24 weeks of dosing and week 25 follow-up, and meet eligibility criteria will be eligible to enter Part 2 (for patients who have not completed dosing and follow-up due to imaging disease progression, please refer to 4.3.1). In Part 2, all patients who complete 24 weeks of dosing and week 25 follow-up will be eligible to enter Part 3 to continue longer treatment and safety follow-up. A patient may be discontinued from treatment if the Investigator assesses that the patient cannot benefit from continued treatment.

Part 3 is an extension treatment phase, and all patients will continue to receive open-label ABSK021 once daily until any of the following events occurs: disease progression, experiencing unacceptable toxicity, withdrawal of informed consent form, commercialization of the study drug for the treatment of TGCT approved by the local regulatory authorities, decision by the sponsor to terminate the study, or until 2 years after the last patient enters Part 3, whichever occurs first.

The study will end when all subjects have completed the study (including completion of all treatments and all visits required by the protocol) or have early withdrawn from the study, or the Sponsor decides to terminate the study, whichever occurs first.

5.9 Concomitant therapy

5.9.1 Permitted Medications

In general, in addition to prohibited medications and treatments specified in the protocol, the Investigator may provide supportive care for disease-related symptoms as clinically indicated, and care should be performed according to the site standard of care procedures. Patients may also receive medication for symptom relief (e.g., antidiarrheals, antiemetics, etc.).

